8.2.2 Secondary Efficacy Endpoints

Continuous endpoint

Change from baseline at 16, 26, 39 and 52 in the followings;

[figure not shown]
- HAQ-DI
- Patient Global Assessment
- %pFVC
- Physician Global Assessment
- mRSS

The above endpoint will be analyzed using mixed-effect model for repeated measures (MMRM). The model will include fixed categorical terms for treatment, randomization strata (autoantibody status of anti-RNA Polymerase III at screening (positive or negative)), visit, and treatment by visit interaction together with continuous covariate terms for baseline value of the endpoint and baseline value by visit interaction. An unstructured correlation structure will be used to model the within-subject variance covariance errors. Should convergence of the model fail (due to the small numbers of subjects in this study), other variance covariance matrices such as autoregressive [AR(1)] correlation matrix will be used if appropriate. The Kenward-Roger approximation will be used to estimate the denominator degrees of freedom. From the model

described above, adjusted (least squares [LS]) means and standard errors will be produced by treatment and visit. Difference in adjusted means at each visit (MT-7117 vs. placebo) with standard errors, 95% CIs and associated P values will also be produced. All available data from all subjects will be used in the analysis without any imputation.

ACR CRISS score responder (CRISS \geq 0.6)

Proportion of subjects with ACR CRISS score responder (CRISS \geq 0.6) at Weeks 16, 26, 39, and 52 will be analyzed using logistic regression model employing SAS GLIMMIX procedure. The model will include fixed categorical terms for the treatment group (TRTPN), the randomization factor (screening autoantibodyanti-RNA Polymerase III, positive or negative - STRTNC), visit, and treatment group (TRTPN) by visit interaction together with continuous covariate terms for baseline mRSS (BLMRSS). The treatment odds ratio at each visit will be estimated using a contrast (using ilink PDIFF options in LSMEANS). An unstructured correlation structure (UN) will be used to model the within-subject variance covariance errors. Should convergence of the model fail (due to the small numbers of subjects in this study), other variance covariance matrices such as autoregressive [AR(1)] or compound symmetry (CS) correlation matrix will be used if appropriate. The following SAS code will be used.

8.2.3 Exploratory Efficacy Endpoints

Continous endpoint

- [REDACTED]
- [REDACTED]
- [REDACTED]
- [REDACTED]
- [REDACTED]

8.3 Safety Assessments

Safety assessments will be made on the SAF population. All data will be listed.

8.3.1 Adverse Events

The overall TEAEs are summarized by Placebo, MT-7117 over all, MT-7117 [REDACTED] only, [REDACTED] to [REDACTED] regimen, [REDACTED] to [REDACTED] regimen for subjects with

- at least one TEAE,
- at least one treatment emergent adverse reaction,
- at least one serious TEAE,
- at least one serious treatment emergent adverse reaction,
- at least one TEAE leading to drug withdrawn,
- at least one treatment emergent adverse reaction leading to drug withdrawn,
- at least one hepatic TEAE,
- at least one hepatic TEAE of Special Interest (AESI)
- at least one hyperpigmentation TEAE,
- at least one Adverse Events of Special Interest (AESI)
- at least one TEAE leading to death.

The frequency and incidence of TEAEs will be summarized by System Organ Class (SOC) and Preferred Term (PT) by Placebo, MT-7117 over all, MT-7117 [REDACTED] only, [REDACTED] to [REDACTED] regimen, [REDACTED] to [REDACTED] regimen. For this table, SOC is sorted by International order; then within SOC, PT is sorted by descending counts under MT-7117 Total group, then descending counts under Placebo group, then alphabetic order for PTs with the same count.

The AE summaries will be presented by treatment group for the following:

- TEAEs by SOC and PT
- TEAEs by SOC, PT and severity
- TEAEs by SOC, PT and relationship to study drug

- Treatment emergent adverse reactions by SOC and PT
- Treatment emergent adverse reactions by SOC, PT and severity
- Serious TEAEs by SOC and PT
- Serious TEAEs by SOC and PT and relationship to study drug
- Serious treatment emergent adverse reactions by SOC and PT
- TEAEs leading to drug withdrawn by SOC and PT
- Treatment emergent adverse reaction leading to drug withdrawn by SOC and PT
- Hepatic TEAEs by SOC and PT
- Hepatic TEAE of Special Interest (AESI) by SOC and PT
- Hyperpigmentation TEAEs by SOC and PT
- TEAEs of special interest by SOC and PT
- TEAEs by SOC and PT for TEAEs with frequency $\geq 5\%$ in total MT-7117 group

For each of the summaries will be done at the subject level - multiple occurrences of the same event within a subject will be counted once in the summaries by SOC and PT; multiple occurrences of the same event within a subject will be counted once in the maximum intensity category (severe > moderate > mild) and/or maximum drug relationship category (reasonable possibility, no reasonable possibility). If intensity or relationship is found to be missing the most severe occurrence will be imputed for that particular summary.

All AEs for each subject, including multiple occurrences of the same event, will be listed.

Deaths that occur during the study will be listed in a data listing. The data listings for serious TEAE and TEAE leading to drug withdrawn and trial emergent adverse event will be generated as well.

The frequency and incidence of TEAEs will be summarized by System Organ Class (SOC) and Preferred Term (PT) by Placebo, MT-7117 over all, Treatment duration (0 to ≤ 3 , > 3 to ≤ 6 , > 6 to < 12 , $= 12$ (months)). For this table, SOC is sorted by International order; then within SOC, PT is sorted by descending counts under MT-7117 Total group, then descending counts under Placebo group, then alphabetic order for PTs with the same count.

The AE summaries will be presented by treatment group for the following:

- TEAEs by SOC and PT
- Serious TEAEs by SOC and PT

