3 STUDY DESIGN

3.1 Study Design

This is a Phase 2, multicenter, randomized, double-blind, placebo-controlled, parallel-group study to evaluate efficacy, safety, and tolerability of MT-7117 in subjects with dcSSc.

The duration of the study is approximately 60 weeks; screening period up to 4 weeks, double-blind treatment period of 52 weeks, and a safety follow-up period of 4 weeks after last dose.

Following completion of the all screening assessments, subjects will return to the clinical site for start of the double-blind treatment period (Visit 2, Day 1) and baseline assessments will be evaluated and confirmed the eligibility (e.g., safety assessments, ACR CRISS components, and nevi (Melanocytic Lesions) evaluation, if nevi (Melanocytic Lesions) are present.

Eligible subjects will be randomized in a 1:1 ratio to either MT-7117 at starting of [REDACTED] every day (QD) or matching placebo in a double-blind manner, stratified by autoantibody status of [REDACTED] performed at screening (positive or negative).

Study drug will be administered once daily orally in the morning with or without food.

During the double-blind treatment period, subjects will return to the clinical site and assessments will be collected as described in protocol.

The decision about dose reduction and tolerability should be made according to the pre-specified criteria and the Investigator's clinical judgment.

If a subject is experiencing intolerance to study drug, they should first be conservatively managed using standard of care and maintain the starting dose of study drug (active or placebo).

If the subject continues to present significant intolerable AEs at the following scheduled or unscheduled visit and the Investigator deems it necessary, the daily dose of study drug can be reduced from [REDACTED] QD to [REDACTED] QD while tolerability is managed with standard of care.

If the subject continues to present significant intolerable AEs at the following scheduled or unscheduled visit and the Investigator deems it necessary, the dose of study drug can be reduced from [REDACTED] QD to [REDACTED] QD.

If the subject continues to present significant intolerable AEs at the decreased dose of [REDACTED] QD and the Investigator deems it necessary, the subject may discontinue study treatment.

All dose reductions during the Treatment Period will be done in [REDACTED] decrements. Dose reductions will be conducted via the Interactive Web-based Response System (IWRS).

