7.1.1.5 Treatment Duration and Compliance

(1) Treatment Duration

Study medication exposure in days will be calculated for each subject using the following:

Treatment duration (days)

=Date of last study drug up-to week 52 – date of first study drug + 1

If the date of the first study drug or the date of the last study drug is missing, the first day of the month will be used.

If the date and month of the first study drug or the those of the last study drug are missing, then the first day of the first month (January) will be used.

Interruptions, compliance, and dose changes are not taken into account for duration of exposure.

(2) Treatment Compliance

Treatment compliance will be calculated using the formula below and reported to 1dp.

Treatment compliance(%)

$$= \frac{\text{Treatment duration (days)} - \text{Days of missed doses} + \text{Days of overdose}}{\text{Treatment duration (days)}} \times 100\%$$

Days of missed doses : Counted days only if the patient does not take at least 1 of the daily dose

of 3 investigational product tablets

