8.1.9 Treatment Duration and Exposure and Treatment Compliance

Treatment duration and Exposure and Treatment compliance will be summarized on the ITT population.

Treatment duration (months) will be calculated by dividing by 30.4375 for treatment duration (days). Then, treatment duration months and Exposure will be summarized as a categorical variable using the following categories:

- 0 to <= 3 months
- > 3 months to <= 6 months
- > 6 months to <= 12 months
- >12 months
- [REDACTED]
- [REDACTED]
- [REDACTED]

The number and percentage of treatment compliance will be calculated using the range 80% <= compliance <= 120% as a subject being treatment compliant. The number and percentage of treatment compliance will be summarized by treatment and and following period.

- Baseline to 15 Study Day
- 16 Study Day to 43 Study Day
- 44 Study Day to 113 Study Day
- 114 Study Day to 183 Study Day
- 184 Study Day to 274 Study Day

- 275 Study Day to 365 Study Day

8.1.10 Interruption/permanent discontinuation of study drug and subject question for study medication

The number and percentage of study drug interruption and study drug permanent discontinuation will be calculated with it's reason by treatment on the ITT population. Interruption duration of study drug will be summarized by treatment on the ITT population. The number and percentage of subject question for study medication will be calculated by treatment on the ITT population.

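### The last band of the AE-by-treatment-duration tables in SAP 8.3.1 is printed as = 12 months: without rounding no whole-day duration can reach it, and 366 days or more has no column

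*SAP*

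**What the plan says.** Four places in the SAP and one in the schedule of activities bear on this.

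- **SAP 8.3.1 (Adverse Events).** TEAEs and serious TEAEs are tabulated by SOC and "Preferred Term (PT) by Placebo, MT-7117 over all, Treatment duration". The bands are 0 to ≤ 3 and > 3 to ≤ 6 months, then "> 6 to < 12 , $= 12$ (months". Nothing is listed above 12.
- **SAP 8.1.9 (Treatment Duration and Exposure).** "Treatment duration (months) will be calculated by dividing by 30.4375 for treatment duration (days"). The two upper bands here are "> 6 months to <= 12 months" and more than 12 months, so every duration has a place. No rounding rule is given for assigning bands.
- **SAP 7.1.1.5 (Treatment Duration and Compliance).** Duration in days is "Date of last study drug up-to week 52 – date of first study drug + 1". "Interruptions, compliance, and dose changes are not taken into account for duration of exposure", so it is the calendar span from first to last dose.
- **SAP 3.1 (Study Design).** The plan is a "double-blind treatment period of 52 weeks".
- **Schedule of Activities (Table 1).** The Week 52 visit is Day 365 ± 7, that is Day 358 to Day 372.

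**The concern.** A set of table bands should place every subject in exactly one column. Here the last band is a single point, 12 months, and the SAP's divisor puts that point between two whole days. A programmer following the text literally would produce an empty last column and have nowhere to put anyone dosed for 366 days or more. Subjects who completed the planned 52 weeks in 365 days or fewer would share a column with subjects who stopped in month 7.

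The stake is modest but real. These are the only tables in 8.3.1 that relate AE incidence to length of exposure, in a trial with 36 subjects planned per arm. The band denominators might not add up to the arm total, and inclusion of a completer could turn on whether the last dose fell a day earlier or later. If the gap is noticed only after unblinding, the repair is post hoc.

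**Working it through.** **Inputs.** Divisor 30.4375 (SAP 8.1.9); whole-day duration, last dose minus first dose plus 1 (SAP 7.1.1.5); bands (SAP 8.3.1 and 8.1.9); Week 52 visit Day 358–372 (Table 1); planned treatment 52 weeks (SAP 3.1). The band label is read as the subject's total treatment duration, the quantity defined in 7.1.1.5. Section 8.3.1 does not say so explicitly.

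**Step 1: the plan's own figure.** 365.25 / 12 = 30.4375, so the divisor reproduces exactly.

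**Step 2: where 12 months falls.** 12 × 30.4375 = 365.25 days. This is not a whole number, so no duration equals 12 months unrounded.

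**Step 3: assign days to bands, months = days / 30.4375, unrounded.**

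| Days | Months | Band in 8.3.1 | Band in 8.1.9 |
|---|---|---|---|
| 182 | 5.980 | > 3 to ≤ 6 | > 3 to ≤ 6 |
| 183 | 6.012 | > 6 to < 12 | > 6 to ≤ 12 |
| 358 | 11.762 | > 6 to < 12 | > 6 to ≤ 12 |
| 364 (52 × 7) | 11.959 | > 6 to < 12 | > 6 to ≤ 12 |
| 365 | 11.992 | > 6 to < 12 | > 6 to ≤ 12 |
| 366 | 12.025 | none | > 12 |
| 372 | 12.222 | none | > 12 |

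Days 183 to 365 fall in the same band in both sections. The sections differ only from Day 366 upward.

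**Step 4: the visit window.** If the last dose is on the visit day, 8 of the 15 permitted days (358–365) fall in > 6 to < 12, 7 (366–372) have no column, and none falls in = 12. If the last dose is the day before the visit, durations run from 357 to 371 and the split is 9 and 6. These are counts of calendar days, not of subjects.

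**Step 5: readings that might rescue the band.**

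- *Duration capped at Day 364 or 365 by the wording* "Date of last study drug up-to week 52": nobody is lost, every completer is in > 6 to < 12, and = 12 is still empty.
- *Rounding to 2 decimals:* = 12 is still empty.
- *Rounding to 1 decimal:* Days 364–366 enter = 12, and Day 367 onward has no column.
- *Rounding to whole months:* Days 351–380 all enter = 12, and nobody in the visit window is lost.
- *The symbol is really ≥ 12:* Day 366 onward has a column and the bands hold the same subjects as those in 8.1.9, but Day 365 and Day 366 are still in different bands.

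**The case against.** The strongest reply is that the defect rests on one character in machine-read text. The band before it, > 6 to < 12, is the natural complement of ≥ 12. An inequality sign is also missing elsewhere in this SAP: the lowest bilirubin cut has a > sign in 7.1.3.2 and none in section 10. That possibility stands, and the PDF must be checked. Against it, the same sentence in 8.3.1 keeps its two ≤ signs. Even with ≥ 12 the completers remain split at Day 365/366, and a subject treated for the planned 364 days is still classed below 12 months.

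A second reply is that rounding to whole months, or a cap at Week 52, means nobody in the visit window is lost. Either could be intended, but the SAP states no rounding rule and does not define the cap. Either would also leave the more-than-12-months band in 8.1.9 empty for everyone within the Week 52 visit window, so neither fits both sections comfortably.

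A third reply, which stands in full, is that the consequence is limited. The same events appear in the main TEAE and serious TEAE tables, all AEs are listed, the exposure table in 8.1.9 covers every duration, and no test or decision uses these bands.

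A reader might go further and infer that most year-long exposure is misplaced or dropped, or that the two sections cannot be matched. The documents do not support this. For 358–365 days, > 6 to < 12 is arithmetically correct under the SAP's formula; what is open to criticism is the cut-point. Turning 7 of 15 window days into 47% of completers, or about 34 of 72 subjects (7/15 × 72 = 33.6), requires evenly spread visits, last dose on the visit day and full completion, none of which is given. The two sections also agree band for band up to Day 365.

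**Conclusion.** The point holds as a minor specification defect in a descriptive safety breakdown. As printed and unrounded, the = 12 months band cannot be filled, and durations of 366 days or more have no column. Subjects treated for exactly 52 weeks are grouped with those who discontinued after 6 months.

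The number of subjects left out cannot be determined from the documents. It is zero if duration is capped at Day 364 or 365; otherwise it depends on when Week 52 visits and last doses fall. The conclusion rests on three assumptions: the printed symbol is correct, the 8.1.9 conversion applies to 8.3.1, and no rounding is used. If the symbol proves to be ≥, the gap closes and only the split of completers at Day 365/366 remains. Neither the primary analysis nor the overall AE tables are affected.

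**What to change.** 1. Check the source PDF for the symbol in the last band of 8.3.1.
2. At minimum, make that band ≥ 12 months. The 8.3.1 bands are then exhaustive and hold the same subjects as those in 8.1.9.
3. Preferably, define one set of bands in days for both sections, for example 1–91, 92–182, 183–357 and ≥ 358. The first two cuts reproduce the present ones (3 × 30.4375 = 91.3 and 6 × 30.4375 = 182.6 days). The last starts at the lower limit of the Week 52 visit window, so that Week 52 completers are grouped together. The value 358 is a choice. If the last dose is normally the day before the visit, a Day 358 visit gives 357 days, so the cut should be set together with item 4.
4. State whether the Week 52 limit on the last dose date means a nominal day (364 or 365) or the actual Week 52 visit, and state that months are not rounded if month bands are kept.
5. Require each treated subject to fall in exactly one band, with band denominators summing to the safety-population total for the arm.

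The cost is a line or two in SAP 7.1.1.5, 8.1.9 and 8.3.1 and one programming format. No new data are needed. The change should be made before unblinding.

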6 STATISTICAL CONSIDERATIONS

6.1 Descriptive Statistics

Continuous data will be summarized descriptively using the number in the analysis set (N), the

number of observations (n), mean, standard deviation (SD), median, minimum and maximum. Categorical data will be summarized using frequency counts and percentages. The denominator for the percentages will be the total number of subjects in the treatment group and analysis population being presented, unless otherwise specified (e.g. on some occasions, percentages may be calculated out of the total number of subjects with available data at a particular visit and/or time point).

Unless otherwise specified, all data will be summarized by analysis visits and treatment group.

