7.1.3 Safety Assessments

7.1.3.1 Adverse Events

All AEs and SAEs will be recorded in the source documents. All AEs and SAEs that occur from the time written informed consent is obtained until the end of the Safety Follow-up Period (4 weeks after the last treatment visit, for safety monitoring) will be recorded in the eCRF.

An AE is any untoward medical occurrence in a subject or clinical investigation subject administered a pharmaceutical product that does not necessarily have a causal relationship with this treatment.

Adverse events will be coded according to the MedDRA version 25.0 or higher.

(1) Treatment Emergent Adverse Events/ Treatment Emergent Serious Adverse Events (TEAEs/TESAEs)

Protocol definition

AEs will be classified as 'treatment-emergent' if they arise following the first administration of study drug in the double blind treatment period (after randomization) or if a predose AE increases in severity following dosing in the double blind treatment period (after randomization).

Analysis rule to determine TEAE using onset date of AEs

An AE is classified as treatment emergent if it newly occurred on or after the first dose of study drug. According to this data handling, for the severity part in the above TEAE definition, the AE with upgraded severity and with the new onset date during the treatment period will be

automatically included as TEAE.

If the AE start date is incomplete, it will be imputed as follows for the purpose of determining TEAE and AE duration:

- If the start date is completely missing, the start date will be equal to the date of the first dose date of study treatment. However, if the stop date is not missing and is before the date of the first dose of study treatment, then the stop date will be used instead of the start date and the AE will not be considered as TEAE.
- If the start date is missing, but the month and year are not missing and are equal to the month and year of the first study dose, then start date will be equal to the date of the first dose date of study treatment. If the month of the start date is not equal to the month of the first study dose, then start date will be equal to the first date of the month of the start date. these events will be considered as TEAE.
- If the start date and month are missing, then the first day of the first month (January) will be used.

If an AE stop date is incomplete, it will be imputed as follows for the purpose of determining TEAE and AE duration:

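### The TEAE tables by total treatment duration group subjects by an outcome that AEs help determine, without numbers at risk or person-time, so they cannot show how risk changes with time on drug

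*SAP*

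**What the plan says.** After the main AE summaries, SAP 8.3.1 adds a further set, for TEAEs and for serious TEAEs, presented by System Organ Class and "Preferred Term (PT) by Placebo, MT-7117 over all, Treatment duration". The bands are "Treatment duration (0 to ≤ 3 , > 3 to ≤ 6 , > 6 to < 12 , $= 12$ (months").

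The other relevant rules are:

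- **Treatment duration** (SAP 7.1.1.5) is "Date of last study drug up-to week 52 – date of first study drug + 1", one number per subject. SAP 8.1.9 converts it to months by dividing by 30.4375.
- **Percentages** (SAP 6.1): "The denominator for the percentages will be the total number of subjects in the treatment group and analysis population being presented", unless otherwise specified. SAP 8.3.1 specifies nothing else for this table.
- **Counting** (SAP 8.3.1): "multiple occurrences of the same event within a subject will be counted once in the summaries by SOC and PT".
- **TEAE rule** (SAP 7.1.3.1): "An AE is classified as treatment emergent if it newly occurred on or after the first dose of study drug". There is no cut at last dose, and AEs are recorded to the end of the 4-week safety follow-up.
- **Follow-up of stoppers** (SAP 3.1, protocol 8.1 and 9.5): subjects who stop study drug are encouraged to remain in the study and complete assessments to Week 52.

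SAP 7.1.3.1 defines time to AE onset separately, but this table does not use it. The readable text of neither document plans a person-time rate, a number at risk or an exposure-adjusted incidence.

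**The concern.** A table of AEs against length of treatment will be read as showing whether risk builds up, settles or stays level over time on drug. The planned columns cannot show that. How long a subject stays on drug is known only after randomization, and AEs help determine it. A subject who stops because of an AE lands in a short column and has an AE for certain. A subject in the longest column got there partly by having no AE that ended treatment. The columns also carry different amounts of time at risk, and no denominator allows for that.

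This is the only readable planned table that relates AE incidence to length of exposure. The trial doses for 52 weeks, whereas protocol 8.2.2 describes 300 mg given to patients for up to 16 weeks. In that earlier Phase 2 study, 300 mg had more TEAEs causing discontinuation than 100 mg or placebo. Unequal stopping between the arms is therefore foreseeable, and it would distort a comparison of the same column across arms.

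**Working it through.** The plan gives no rate or column count for this table, so there is no stated figure to reproduce.

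**1. Time on drug.** 12 months against 3 months (the limit of the first band) is 12/3 = 4.0. Against 1.5 months it is 12/1.5 = 8.

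**2. AE observation time.** Safety follow-up adds 28/30.4375 = 0.92 month.

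- Leaves 28 days after last dose, stopped at 3 months: (12 + 0.92)/(3 + 0.92) = 3.3.
- The same, stopped at 1.5 months: 12.92/2.42 = 5.3.
- Stops drug but stays in the study to the end: about 1.

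**3. Column percentages under a constant rate.** The rates are assumptions; the documents give none. AEs occur at 0.10 per month in everyone, each AE stops treatment with probability 0.15, and other stops occur at 0.01 per month.

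- Stopping rate: 0.10 × 0.15 + 0.01 = 0.025 per month. AEs that do not stop treatment: 0.10 × 0.85 = 0.085 per month.
- Share of stops due to an AE: 0.015/0.025 = 0.6. These subjects all have a TEAE.
- Expected subjects per arm of 36, as 36 × [exp(−0.025a) − exp(−0.025b)]: 2.6, 2.4 and 4.3 in the three shorter bands, and 36 × exp(−0.3) = 26.7 completers.

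*AEs counted to last dose.* Completers: 1 − exp(−0.085 × 12) = 63.9%. Stoppers in band a to b: 0.6 + 0.4 × (1 − E), where E = (0.025/0.11) × [exp(−0.11a) − exp(−0.11b)]/[exp(−0.025a) − exp(−0.025b)]. E is 0.884, 0.685 and 0.473.

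*AEs counted to 28 days after last dose.* Multiply E by exp(−0.092). Completers: 1 − exp(−1.02 − 0.092) = 67.1%.

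*All stoppers followed to Week 56 (12.92 months).* Replace E by G = exp(−1.292) × (0.025/0.010) × [exp(−0.010a) − exp(−0.010b)]/[exp(−0.025a) − exp(−0.025b)]. G is 0.281, 0.294 and 0.314.

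| AEs counted | ≤3 | >3 to ≤6 | >6 to <12 | Completers |
|---|---|---|---|---|
| To last dose | 64.6% | 72.6% | 81.1% | 63.9% |
| To last dose + 28 days | 67.7% | 75.0% | 82.7% | 67.1% |
| To Week 56 in all | 88.8% | 88.2% | 87.4% | 67.1% |

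The true rate is the same in every cell. The first row rises and then falls. The last row has equal observation time, yet stoppers look about 20 points worse than completers.

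**4. The base.** The table above uses the subjects in each column as the base. If SAP 6.1 is applied literally and the whole arm is the base, the first row becomes 64.6% × 2.6/36 = 4.7% in the first column and 63.9% × 26.7/36 = 47.4% among completers. That contrast mostly reflects column size.

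**5. The proposed alternative.** With onset periods and time counted until first event or end of observation, the expected first-event rate under these assumptions is 0.10 per month in every period, or 10 per 100 person-months.

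**6. Band limits, a separate matter.** Exactly 12 months is 12 × 30.4375 = 365.25 days, which no whole number of days gives. Without rounding, 364 and 365 days (11.96 and 11.99 months) fall in the third band and 366 days or more falls in none. The completer column above is therefore the evident intent of the last band. Correcting the limits would leave steps 1 to 4 as they are.

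**The case against.** The best case against the point has four parts.

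- **Observation is not the same as drug time.** A reader might infer that AE observation differs four-fold between columns, or that early stoppers are watched for at most 3 months. The documents do not support that. TEAEs are not cut at last dose, and stoppers are encouraged to stay to Week 52. Four-fold is right for time on drug only. This stands, but it does not rescue the table. With everyone followed to Week 56 the first three columns become flat and a gap of about 20 points to completers remains, because AE-driven stopping selects who is in each column.
- **No fixed direction.** A reader might also infer that incidence must climb with time on drug by construction. It need not: the direction depends on AE-driven stopping and on retention. This stands too.
- **The columns might be onset periods.** SAP 8.3.1 does not say outright. But treatment duration is a defined subject-level term, onset time is defined separately, and a band equal to 12 months cannot be an onset interval. Total duration is the better supported reading, though it is inferred.
- **Low consequence.** The tables are descriptive, with no test or decision rule, and non-completer columns may hold only 2 to 4 subjects per arm. All AEs are listed, discontinuations with reasons are summarised by treatment, and the iDMC works from a separate plan that is not available here. This limits the weight of the point. It does not make the columns interpretable.

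**Conclusion.** The point holds as a minor one. Followed as written, SAP 8.3.1 yields two tables whose columns are defined by a post-randomization outcome and whose percentages have no time-at-risk denominator. They cannot show how AE risk changes with time on drug, and fixing the band limits would not change that.

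The two ratios in steps 1 and 2 follow from the plan's own definitions. The percentages rest on assumed rates and on reading the columns as total duration. They show that a false pattern can arise and can change shape with the follow-up assumption; they do not predict its size or direction in this trial. The by-arm and by-regimen TEAE tables and the efficacy analyses are not touched.

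**What to change.** Replace the total-duration columns in the two SAP 8.3.1 tables with AE onset periods, split identically for placebo and MT-7117. For each period and arm, give:

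- subjects at risk at the start of the period (still observed, with no earlier event of that term);
- person-time in the period;
- first events per 100 person-months.

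State one at-risk window, for example to last dose plus 28 days, with observation to end of study as a second display. Use one set of period limits that covers every possible day, and reconcile it with the duration bands in SAP 8.1.9. Add overall exposure-adjusted incidence by arm for TEAEs and serious TEAEs.

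The cost is SAP wording and the reprogramming of two descriptive tables from AE onset and dosing dates already collected. No new data are needed. This is a cheap improvement.
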